3.1 Study Overview This proposal is a 12-week, double-blind, randomized, placebo controlled study of a standardized extract of WSE (target dosage: 1000 mg/day) added to ongoing antipsychotic treatment in mild to moderately symptomatic patients with either schizophrenia or schizoaffective disorder.

Treatment will begin on day 1 at 250 mg oral route, BID. (500 mg/day WSE or placebo) and titrated to 500 mg, po; BID (1000 mg/day) in week 2, for the rest of the study, unless tolerability issues dictate a lower dosage. Psychopathology and adverse events will be assessed at every visit. High sensitivity C-reactive protein (hs-CRP) and other inflammatory markers will be measured at baseline and end of the study.

3.2 Timelines, Visits, Assessments, Rating Scales, Study Medications, Laboratory and EKG and Adherence

After obtaining written informed consent, patients will be screened for eligibility and those who meet all the inclusion and exclusionary study criteria will be randomly assigned (in a 1:1 allocation ratio) to receive double-blind adjunctive treatment either with WSE or placebo for 12 weeks (Visits 2 through 8) see table below describing Schedule of Events. Participants will be seen at scheduled visits unless they

need to be seen sooner. The screening and consenting visits and visit 8 will last nearly 2 hours; the other visits will last about 60 minutes.

3.3 Recruitment Targets and Timelines

3.4 Schedule of Events

Approximate Visit Intervals	V1	V2	V3	V4	V5	V6	V7	V8
				2 wks	4 wks	6 wks	8 wks	10 wks
Informed Consent, Urine Drug Test, Pregnancy test, Psychiatric		X						
Diagnosis and History, Medical History								
Labs, EKG ¹		X						X
PANSS, CGI, PSS ²	X	X	X	X		X		X
MCCB		X				X		X
BP, Pulse, Temperature Weight, Height ³	X	X	X	X	X	X	X	X
Sensoril or Placebo		X	X	X	X	X	X	X
Treatment Emergent Adverse Events or Serious Adverse Events			X	X	X	X	X	X

Visit Comments, Pill Counts ⁴	X	X	X	X	X	X	X	X
--	---	---	---	---	---	---	---	---

Visit 1 can be split up (if needed) into 2 visits for screening and spread over 1 to 4 weeks. Visit 2 is the randomization visit. Following randomization, visit intervals for V3 through V8 can range from \pm 4 days of the expected between interval visits; exceptions on a case by case basis by the study team.

Visits 1 and 8 will last roughly 2 hours. Visits 2, 3, 4, 5, 6, and 7 will last roughly 1 hour.

At Visit 1 – Urine drug test for illicit substances will occur as will a serum pregnancy test for women in the reproductive age group.

¹Labs: CBC + Diff, Chemistry 14? (including liver and renal functions, electrolytes, blood sugar, and lipid profile), urine analysis, and hs CRP and serum for cytokine panels

¹EKG: standard EKG

² The Positive and Negative Syndrome Scale (PANSS), Clinical Global Impression Scale (CGI), Perceived Stress Scale (PSS),

³ Height at screening only, waist circumference and BMI at screening and visit 8 or end of study.

⁴ Pill Counts – will start at visit 3, i.e., post randomization

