7.2. Study Treatments, Assessments and Follow up

After all screening procedures have been completed and reviewed and the participant remains eligible for the study, the participant will receive either Sensoril® or placebo at visit 2. The

participant will get one of these medicines by chance (like flipping a coin), and have a 1 in 2 chance of getting either Sensoril® or placebo. The medicine is packaged identically so that it is not possible to tell which is Sensoril® or which is placebo. The medicine will be given to the participant as capsules, and is taken by mouth. Starting at 1 capsule twice daily, the medicine (or placebo) will be increased to 2 capsules twice daily a week later, unless the participant is experiencing side effects. Neither the participant, or the doctor or the research staff will know if the participant is receiving Sensoril® or placebo.

If any tolerability issues emerge, further titration of study medicines can be stopped at a minimum 500 mg/day. If dosage has been increased to 1000 mg/day it can be decreased to 500 mg/day for side-effects.

Details of procedures at each visit (Visit 1 to 8) are described in the schedule of events (**3.2.c.**). Psychopathology ratings (details of the scales were described in **Section 3.2.d** earlier) are briefly mentioned in section 7.1.a. Safety assessments will include determination of side effects at each visit, and depending on the side effects, further clinical action will be undertaken. Laboratory measures at baseline and end point will provide more safety data as will careful monitoring of physical and psychological status at each visit.

If the participant would like to know the treatment assignment at the end of the data analyses and if a contact address or phone number is left with research staff, we will attempt to notify them of their treatment assignment during the study.

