7.3. Efficacy and Safety Assessments

As noted in the Schedule of Events table, psychopathology (PANSS, CGI) and stress (PSS) scales will be assessed at every visit and will form the measurements required for affirming the primary efficacy outcomes, and will inform future studies about the size of the WSE treatment effects. These scales will also assist in monitoring psychopathology and stress as safety concerns.

Psychotropic Medications

These medications are listed in the database by name, daily dosage, start and stop dates. This will permit coding of increases (or decreases) in doses of existing medications, stopping of existing medications (e.g. stopping an existing antipsychotic and starting a new one), etc. Further discussion of the data analysis is provided in section 9.1.c – Psychotropic Medication End Points

Safety Assessments

During the screening process, a review of the medical history, recording of vital signs, laboratory and EKG assessments will provide safety data to the PI and research staff, and help them assess suitability of the subject for the study.

Side-effects will be monitored at each visit, by asking an open ended question and following up with the MPRC Side Effect Checklist. Based on the nature of the side effects, these may be attended to by either reducing the dosage, discontinuing study capsules, with follow-up

laboratory and/or physical examinations, or consultations, until resolution occurs. Recording of vital signs, the use of psychopathology and stress rating scales will further assist in evaluating safety of participating participants.

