7.4. Data and Safety Monitoring Board (DSMB)

The MPRC has established a Data and Safety Monitoring Board (DSMB), which is comprised of two psychiatrists, a statistician, a pharmacist, and a community representative. The psychiatrists are experts in the clinical treatment of people with schizophrenia. None of the DSMB members reviewing this study will be investigators on the proposed project; however, [name] serves as a non-voting member of the DSMB to assist in the monitoring of all MPRC trials. The DSMB will be charged with the following responsibilities: 1) to review the proposed protocol; 2) to monitor study progress and the occurrence of side effects/adverse events, and serious adverse events throughout the course of the study; and 3) to review with [name], the statistician for the project, the study data management system. The DSMB will review reports on protocol progress, side effects and adverse events at least once a year. In addition, all serious adverse events (SAEs) will be reported to the DSMB, [name], and the University of Maryland School of Medicine IRB. [name] will receive all SAE reports within 24 hours of their occurrence. The DSMB and University of Maryland School of Medicine IRB will receive the reports within 48 hours. If the incidence of any side effect/adverse event is 25% or more or any SAE occurs in excess in either treatment group, then the DSMB will notify the P.I.s. The P.I.s and DSMB will determine whether possible protocol modifications are required to minimize the further occurrence of such events.

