8.5. Safety Analysis

Safety analyses of vital signs, laboratory measures, body weight etc. will be evaluated for the safety population, either as continuous or categorical variables (for instance – normal, abnormal etc). Further, the treatment-emergent adverse events will be grouped by organ-system and tabulated by treatment assignment, and rates between treatments will be compared using contingency statistics (chi-square or other Fishers Exact test) for categorical variables and T-tests for continuous variables.

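### The schedule and the text disagree on whether side effects are asked about before the first dose, and neither the treatment-emergent analysis nor the 25% DSMB rule is tied to a pre-dose record

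*Combined protocol and SAP*

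**What the plan says.** The adverse-event row of the Schedule of Events (3.4), "Treatment Emergent Adverse Events or Serious Adverse Events", carries marks at V3 to V8 and none at V1 or V2. The notes to the table state that "Visit 2 is the randomization visit", and section 7.2 has study capsules handed out at that visit. V2 is therefore the last visit at which a pre-dose record can be made.

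The text reads differently:

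- Section 3.1: "Psychopathology and adverse events will be assessed at every visit".
- Section 7.2: "Safety assessments will include determination of side effects at each visit".
- Section 7.3, the only section that names the instrument: "Side-effects will be monitored at each visit, by asking an open ended question and following up with the MPRC Side Effect Checklist". The checklist has no row of its own in the schedule.

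For the analysis, section 8.5 says that "the treatment-emergent adverse events will be grouped by organ-system and tabulated by treatment assignment" and compares the rates between arms. Treatment-emergent is not defined there or in section 7.5, whose definition of an adverse event has no criterion of onset or worsening. The DSMB rule in section 7.4 begins "If the incidence of any side effect/adverse event is 25% or more". Reaching it leads to notification of the principal investigators and a joint review. Inclusion criterion (e) in section 4.3 requires at least 4 weeks of antipsychotic treatment before entry.

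**The concern.** Everyone enters on antipsychotics, and other psychotropic drugs are allowed and recorded, so some checklist symptoms can be expected before the first study capsule. A site that works from the schedule first asks at V3. A participant sedated for months before entry and one who became sedated on study capsules then give the same answer. A site that works from sections 3.1, 7.2 and 7.3 may have a V2 record, so the two sites could hold different data.

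Three things are at stake: how clearly a tolerability signal shows in the 8.5 comparison, how much the 25% rule tells the DSMB, and a baseline that cannot be recovered once dosing has started.

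**Working it through.** **Passages side by side.** The schedule implies first assessment at V3. Sections 3.1, 7.2 and 7.3, read literally, include V1 and V2. None of them says that the checklist comes before the first capsule at V2, and none says how a symptom already present is to be counted. Choosing one reading of the timing therefore does not supply the missing rule.

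**Number per arm.** Section 8.6 gives 33 per arm at effect size 0.83, with power 0.95 (1-tailed 0.05) and 0.90 (2-tailed). A two-sample t-test gives 0.955 and 0.913 at 33 per arm, so the plan's figure reproduces. I use 33 per arm for safety as well, which assumes no loss from the safety population.

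**Model for the arm comparison (assumed; the documents give no side-effect rates).** Let b be the share of participants with the symptom before dosing, equal in both arms and persisting. Let e be the new-onset rate among those without it. Suppose every pre-existing symptom is recorded as an event.

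- Raw count: b + (1 − b)e
- New events only: (1 − b)e
- Risk difference under either count: (1 − b)(e₁ − e₀)

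With b = 0.30 and two-sided exact Fisher power at 0.05:

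| New onset, WSE vs placebo | Count | Rates | Difference | Ratio | Power |
|---|---|---|---|---|---|
| 40% vs 5% | raw | 58.0% vs 33.5% | 24.5 points | 1.7 | 0.46 |
| 40% vs 5% | new only | 28.0% vs 3.5% | 24.5 points | 8.0 | 0.72 |
| 20% vs 5% | raw | 44.0% vs 33.5% | 10.5 points | 1.3 | 0.10 |
| 20% vs 5% | new only | 14.0% vs 3.5% | 10.5 points | 4.0 | 0.13 |

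For 40% vs 5%, raw and new-only power at other backgrounds are 0.73 and 0.88 (b = 10%), 0.58 and 0.82 (20%), and 0.35 and 0.60 (40%).

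**The 25% rule.** 8/33 = 24.2% and 9/33 = 27.3%, so an arm reaches the threshold at 9 events. For one symptom recorded at rate p in both arms with no drug effect, the one-arm chance is P(X ≥ 9), X ~ Bin(33, p). The either-arm chance is 1 − (1 − P)².

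| Recorded rate p | One arm | Either arm |
|---|---|---|
| 10% | 0.4% | 0.8% |
| 15% | 5.0% | 9.6% |
| 20% | 20.0% | 36% |
| 25% | 44.7% | 69% |
| 30% | 69.6% | 91% |

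Now take a 5% new-onset rate in both arms on top of the background. At b = 20% the recorded rate is 0.20 + 0.80 × 0.05 = 24%, and the either-arm chance is 63%. Counting new events only, the rate is 0.80 × 0.05 = 4% and the chance is below 0.001%.

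**The case against.** The case on the other side has five parts.

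- **The text already requires it.** Three sections say every or each visit, and V2 is a visit. Nothing can be treatment-emergent before dosing, so blank V1 and V2 cells fit the row's label. The table as extracted may also have shifted columns: consent and pregnancy testing appear under V2, while the notes put the drug and pregnancy tests at Visit 1. This stands against reading the blanks as proof that side effects are recorded only from V3. It does not remove the contradiction (the six marks fit V3 to V8) or supply a pre-dose instruction.
- **Other pre-dose data exist.** Section 7.3 says that "a review of the medical history, recording of vital signs, laboratory and EKG assessments will provide safety data"; PANSS, CGI and PSS are rated at V1 and V2, and psychotropic drugs are recorded at entry. A reader might infer that new and old symptoms cannot be separated at all. The documents do not support that. These sources are, however, no item-by-item baseline for the checklist.
- **The placebo arm handles background.** Largely right. A reader might infer that the arm comparison is biased towards no difference. In the model above the risk difference is the same under either count. What suffers is the ratio and the power.
- **The gain may be small.** Also right for modest effects: at 20% vs 5% the limit is 33 per arm, not the counting rule.
- **The 25% rule is mild.** A reader might infer that background symptoms will set it off. The documents give no background rate, the rule speaks of incidence, which in ordinary use means new cases, and it leads only to notification and review. But incidence in that sense needs a pre-dose record to be applied consistently.

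**Conclusion.** The point holds as an unreconciled contradiction about timing plus a missing baseline rule. A site following the schedule would lose a pre-dose record that cannot be rebuilt, and pre-existing side effects could then not be reliably told from new ones within a participant.

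The size depends on rates that the documents do not give. With 30% background, the power cost ranges from substantial (0.46 against 0.72) for a large drug effect to negligible (0.10 against 0.13) for a modest one. The 25% rule is hardly affected at a recorded rate of 10% and becomes uninformative for symptoms at about 20% to 30% or more. These figures assume 33 per arm in the safety population, equal and persistent background in both arms, and every pre-existing symptom recorded as an event. The primary efficacy analysis is not affected. The change is worth making because it is cheap and is only possible before dosing.

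**What to change.** 1. Reconcile the Schedule of Events with sections 3.1, 7.2 and 7.3: mark the open question and the MPRC Side Effect Checklist at V2, to be completed before the first dose, and give the checklist its own row.
2. In section 8.5, count an event as treatment-emergent only if it is new or more severe than at V2.
3. In section 7.4, state that the incidence reported for the existing 25% notification is calculated on the same basis, per arm.

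The cost is a few minutes at V2 with a form the sites already use, one schedule change, and a sentence each in 7.4 and 8.5. Reported event rates will be lower than a raw count, so the report should state the definition beside them.

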3.5 Outcome Instruments

Psychopathology will be assessed using the Positive and Negative Syndrome Scale that measures the severity of psychotic and non-specific symptoms and is commonly used in

schizophrenia clinical trials, and a global assessment of the severity of illness (CGI) as well as change, i.e. improvement or worsening. The Perceived Stress Scale (PSS) will also be utilized.

Positive and Negative Syndrome Scale (PANSS): (Kay, Fiszbein et al. 1987) The PANSS is a psychiatric scale used for measuring symptom severity of patients with schizophrenia. It is widely used in clinical trials in schizophrenia. The scale measures the two main types of symptoms in schizophrenia; positive symptoms, which refer to an excess or distortion of normal functions (e.g., hallucinations and delusions), and negative symptoms, which represent a diminution or loss of normal functions (e.g. speech, activity, motivation, etc.). The PANSS is a relatively brief interview, requiring 20-30 minutes to administer. The interviewer will be trained to a standardized level of reliability.

Clinical Global Impression Scale: (Guy 1976) The Clinical Global Impression Scale (CGI) for Severity and Change subscales is an assessment of the clinical impression of the severity of illness and the change in severity of symptoms. A severity score of 1 indicates subject is normal, not ill, 2 indicates borderline mentally ill, 3 indicates mildly ill, 4 indicates moderately ill, 5 indicates markedly ill, 6 subject indicates is severely ill and 7 indicates the subject is among the most extremely ill. Improvement or worsening or no change is noted in the change subscale. The CGI is widely used in clinical trials in psychiatry.

Perceived Stress Scale (Cohen, Kamarck et al. 2000) The Perceived Stress Scale (PSS) was developed to measure of the degree to which situations in one's life are appraised as stressful. Psychological stress has been defined as the extent to which persons perceive (appraise) that their demands exceed their ability to cope. The PSS has become one of the most widely used

psychological instruments for measuring perceived stress. It has been used in studies assessing the stressfulness of situations, the effectiveness of stress-reducing interventions, and the extent to which there are associations between psychological stress and psychiatric and physical disorders. Based on studies, the PSS predicts both objective biological markers of stress and increased risk for disease among persons with higher perceived stress levels.

MATRICS Consensus Cognitive Battery (MCCB) (Nuechterlein et al, 2008) The MCCB is intended to provide a relatively brief evaluation of key cognitive domains relevant to schizophrenia and related disorders. It was designed as an outcome measure for use in schizophrenia clinical trials. The MCCB is comprised of 10 tests, which assess seven cognitive domains. The MCCB composite score is a standardized mean of the seven domain scores. T-scores are standardized to normative data, and have an estimated mean of 50 and SD of 10 in the general healthy population. The administration of the MCCB takes approximately 70 minutes. The MCCB will be administered at baseline, week 6 and week 12.

3.6 Psychotropic Medications

Medications prescribed for psychiatric symptoms (antipsychotic agents, anti-depressants, anxiolytic and hypnotic agents, lithium and anticonvulsants) are captured at entry to the study and changes are recorded at each visit. Changes in medications, such as increases or decreases in dosages, addition of a new agent, or stopping an agent will be coded for in the statistical analyses. Further details are provided in Section 7.1.a (Efficacy and Safety Assessments) and Section 9. (Statistical Methods/Data Analysis) and 9.1.c. Psychotropic Medication Endpoints.

3.7 Laboratory Measures

Laboratory parameters will include the Complete Blood Count (CBC) with differential, a standard Chemistry 14 panel or similar that includes hepatic and renal functions, electrolytes, blood sugar, and lipids). A urine analyses will provide safety data necessary for inclusion or exclusion of study subjects. Women in the reproductive age group will have blood drawn for a serum pregnancy test which is an exclusion criterion. A urine drug test will be performed at baseline for illicit substances and the results of this testing will also assist in excluding or including subjects. An EKG will be read by a qualified physician.

Bloods will be drawn at baseline and endpoint to allow for hs-CRP and measures of inflammatory and related markers. This will include 1 tube for the hs-CRP to be sent to Quest (or other) commercial laboratory. Two other tubes (EDTA) will be drawn, centrifuged and 2 aliquots from each tube will be stored on freezer tube (total 4 cytokines and inflammatory marker aliquots).

Serum or plasma hs-CRP will be measured. (Please see *Schedule of Events*).

3.8 A review of medical conditions will be conducted by research staff including medical history and medications received for various medical conditions will be recorded. Vital signs will include blood pressure, pulse, height and weight. Laboratory tests and EKG, as noted in the Schedule of Events Table, will be conducted as part of the screening and safety assessments. Women of reproductive age will have a serum pregnancy test at screening. A psychiatric history using the SCID will be conducted, and if needed additional history from the treating clinicians and/or review of medical charts will be obtained to confirm the psychiatric diagnosis.

Once the subject is randomized, adherence will be monitored by pill counts during visits, i.e., the difference in the number of pills the participant should have taken during the visit interval versus those reported as taken by the participant. Participants will be counseled to bring back pill containers at each visit.

4. Participant Selection

4.1 Human Participant Involvement and Characteristics.

The total number of participants to be randomized will be 66, which will male and female adults with DSM 5 schizophrenia or schizoaffective disorder, of any race and between the ages of 18-64. We anticipate screening nearly 90 people in order to obtain 66 participants who meet the inclusion/exclusion criteria and provide evaluable data. This number is based on an anticipated screen failure rate of 25%. Participants will be research subjects from MPRC (N=33) and UCLA (N=33).

We intend to recruit participants whose symptoms are in the mild to moderate range, whose antipsychotic medications have been received for \geq 4 weeks and who do not require imminent hospitalization. In addition, participants will have had a recent positive symptom exacerbation prior to study entry. (Please see inclusion/exclusion criteria for details.)

4.2 Sites and Method of Recruitment

The study sites will be the research programs at UCLA and the MPRC. As in past studies from these sites, the psychiatrists and clinicians will be provided information about the study.

Potential research participants may be first identified by their physician/clinical care team. The clinician will discuss the research project with the potential participant.

For people who contact the research team directly in response to IRB-approved advertisements, a telephone screen is conducted. The nature of the questions asked in the research screening interview are fairly consistent with the standard operating procedures for determining the need for treatment for any person whether research eligible or not.

Recruitment will also be sought from the UCLA and MPRC registries of previous research participants who consented to be recontacted.

If the potential participant can provide informed and competent consent to participate in the study, and wishes to participate, the full consent document will be signed by the person, and the study physician or research staff will sign the certification statement on the consent at the time of obtaining the consent. Consenting will include a quiz prior to signing to ensure the participant understands all procedures.

Should any change in the risk/benefit ratio occur after the person has begun to participate in the study, the participant will be informed of the new information. Once the investigator is notified of the change, all participants will be told verbally about the new information. Once the consent has been revised to include the change and the document is approved by the IRB, the new consent form will be reviewed with each participant and signed by him/her if he or she wishes to continue to participate in the study.

The study protocol specifies two sets of criteria for participation: inclusion criteria, and exclusion criteria, which are listed below:

